### 6.2.2. Anticipated Adverse Events

The following are anticipated adverse events related to the device and procedure that will be documented:

**Table 1: Anticipated Adverse Events**

Event	Comment	Consequence
Aspiration pneumonia	During procedure	Treat with antibiotics
Nausea, vomiting, abdominal pain, abdominal spasms, hiccups, heartburn, belching	all expected symptoms that can occur in varying degrees in almost all balloon patients	Mild dehydration Occasionally requires IV hydration
Blood tinged vomitus	Small amounts less than a tablespoon	None
Vomiting blood	Large amounts due to esophageal tear – “Mallory-Weiss Tear” - or due to ulcer of esophagus or stomach.	Requires balloon extraction and possible endoscopic clips to close tear or stop bleeding from ulcer
Superficial mucosal bleed	Tongue, esophagus or stomach during procedure	Small amounts – evaluated by PI and generally not clinically significant
Heartburn, acid reflux	Treated with medications (PPI, antacids, metoclopramide, sucralfate)	If uncontrolled, balloon down volume adjustment can help
Diarrhea	Due to bacterial overgrowth-like syndrome. Occurs in 20% of subjects and may recur	Treat with metronidazole 500 mg 3 times daily for 5 days
Esophageal or stomach ulcer	Superficial ulcers can be treated with medications (PPI, antacids, sucralfate)	Larger ulcers may require balloon extraction
Esophageal tear	During implantation or extraction	May require endoscopic clips
Balloon deflation	Urine turns blue alerting subject to deflation	Deflated balloon will remain in stomach or pass in bowels uneventfully. Rarely the balloon will obstruct intestine
Bowel Obstruction	Deflated balloon that obstructs intestine on its way out	Requires endoscopic extraction or surgery
Perforation of esophagus	Dr error- Balloon inflated in esophagus, or perforation during extraction	Requires endoscopic clips or surgery
Perforated stomach	Spontaneous ischemic perforation or perforated ulcer	Requires endoscopic clips or surgery

Event	Comment	Consequence
Infected balloon fluid	Unexpected dilation of balloon with air/fluid level in balloon	Requires balloon removal and culture of fluid

The investigator will document the clinical significance of all abnormal laboratory findings in the source documents throughout the study. The investigator will exercise his/her medical judgment in deciding whether an abnormal laboratory finding or other abnormal assessment is clinically significant. However, if in the opinion of the investigator, the frequency or severity of the event is greater than would be expected then it must be reported as an AE.

**6.2.3. Procedures for recording adverse events**

It is the responsibility of the local investigator to ensure that all adverse events (AEs, ADEs, and device deficiencies) occurring during the course of the study are recorded. This may include but not be limited to:

- A description of the event
- The dates of the onset and resolution
- Action taken
- Outcome
- Initial assessment of relatedness to the device (final adjudication will be made by the DMC)
  - a. Whether the AE is serious or not
  - b. Whether the AE arises from device deficiency
  - c. Whether the AE arises from user error

Adverse events that occur during the course of the study should be treated by established standards of care that will protect the life and health of the study subjects

It is the responsibility of the local investigator to collect all directly observed adverse events and all adverse events spontaneously reported by the subject. In addition, each subject should be questioned about adverse events at each visit. Adverse events should be recorded on provided serious adverse event data collection forms.

**6.2.4. Reporting Procedures for Adverse Events and Serious Adverse Events**

It is the responsibility of the local investigator to ensure that all adverse events which fall into the categories of SAEs, DRAEs, SDRAEs and any device deficiencies are reported to the sponsor as soon as possible after becoming aware of the event but no later than 24 hours, via e-mail to the sponsor at [[contact]](mailto:[contact]) (cc to [[contact]](mailto:[contact])) using the provided SAE form.

A sponsor who conducts an evaluation of an unanticipated adverse device effect under 812.46(b) shall report the results of such evaluation to FDA and to all reviewing IRB's and participating investigators within 10 working days after the sponsor first receives notice of the effect. Thereafter the sponsor shall submit such additional reports concerning the effect as FDA requests.

### **6.3. Study Suspension or Early Termination**

#### **6.3.1. General**

The DMC or sponsor may recommend suspension or termination of the study either at an individual investigation site or the entire study for significant and documented reasons. An investigator, IRB or FDA may suspend or prematurely terminate participation in the study at the investigation sites for which they are responsible. If suspicion of an unacceptable risk to subjects arises during the study, or when so instructed by the IRB or regulatory authorities, the sponsor shall suspend the study while the risk is assessed. The sponsor shall terminate the study if an unacceptable risk is confirmed.

#### **6.3.2. Stopping Rule for Gastric Ulcer**

At each DMC meeting, the crude rate of gastric ulcers will be calculated using as its denominator only subjects who have been implanted for at least 2 months plus all subjects implanted less than 2 months but had experienced a gastric ulcer event. A gastric ulcer event is defined as a gastric lesion  $\geq 5$ mm in diameter with unequivocal depth by endoscopy. The date of the event will be the date of the confirmatory endoscopy.

If the crude gastric ulcer rate exceeds 10% then a Kaplan-Meier curve will be calculated that includes all implanted subjects. Subjects who are ongoing at this time without having experienced a gastric ulcer event will be censored at the data cutoff date, and subjects who terminated from the trial due to any reason other than a gastric ulcer event will be censored at the time of explant. Rates at each monthly interval for which a minimum of 25 subjects have been implanted will be calculated. For example, if 30 subjects have been implanted for at least 3 months, but only 20 for at least 4 months then rates will be calculated for 1, 2, and 3 months only. If the monthly Kaplan-Meier rate exceeds 20% for any month, then the study will be suspended and the IRB and FDA will be notified.

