## **6. DATA MONITORING AND SAFETY REPORTING**

### **6.1. Data Monitoring Committee**

An independent Data Monitoring Committee (DMC) will serve as an autonomous advisory group for Spatz FGIA, Inc., the sponsor of this trial. The DMC will be responsible for safeguarding the interests of trial participants, assessing the safety and efficacy of the interventions during the trial, adjudication of Adverse Events, and for monitoring the overall conduct of the clinical trial. The DMC may also provide recommendations about stopping or continuing the trial. To contribute to enhancing the integrity of the trial, the DMC may also formulate recommendations relating to the selection/recruitment/retention of participants, their management, improving adherence to protocol-specified regimens and retention of participants, and the procedures for data management and quality control.

The DMC members appointed for this trial consist of individuals who collectively have experience and expertise in the management of patients with obesity, experience in randomized clinical trials with experimental agents/devices, experience in safety monitoring and absence of significant conflicts of interest.

The first DMC meeting will occur once 25 subjects have either been implanted for at least 2 months or have terminated from the trial. Subsequent DMC meetings will be scheduled based on the following assessment of gastric ulcer rates.

At each DMC meeting, the crude rate of gastric ulcers will be calculated using as its denominator only subjects who have been implanted for at least 2 months plus all subjects implanted less than 2 months but had experienced a gastric ulcer event. A gastric ulcer is defined as a gastric lesion  $\geq 5$ mm in diameter with unequivocal depth by endoscopy. The date of the event will be the date of the confirmatory endoscopy. If this rate exceeds 10% then a Kaplan-Meier curve will be calculated that includes all implanted subjects. Subjects who are ongoing at this time without having experienced a gastric ulcer event will be censored at the data cutoff date, and subjects who terminated from the trial due to any reason other than a gastric ulcer event will be censored at the time of explant. Rates at each monthly interval for which a minimum of 25 subjects have been implanted will be calculated. For example, if 30 subjects have been implanted for at least 3 months, but only 20 for at least 4 months then rates will be calculated for 1, 2, and 3 months only.

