If all of the monthly rates of gastric ulcers are below 10%, the DMC will meet every two months. If any of the monthly rates of gastric ulcers exceeds 10%, the DMC will meet every month.

A separate DMC charter will contain full details of the committee and its roles and reporting structure.

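### The Kaplan-Meier ulcer rates are calculated only after a crude rate passes 10%; during accrual this can delay the monthly-meeting trigger, and less often the 20% suspension check

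*Combined protocol and SAP*

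**What the plan says.** Section 6.3.2 starts from a crude ulcer rate, "using as its denominator only subjects who have been implanted for at least 2 months plus all subjects implanted less than 2 months", the latter only if an ulcer has already been found. Then: "If the crude gastric ulcer rate exceeds 10% then a Kaplan-Meier curve will be calculated that includes all implanted subjects". Section 6.1 repeats the condition: "If this rate exceeds 10% then a Kaplan-Meier curve will be calculated".

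Both actions depend on the curve:
- Suspension (6.3.2): "If the monthly Kaplan-Meier rate exceeds 20% for any month, then the study will be suspended".
- Meeting frequency (6.1): "If any of the monthly rates of gastric ulcers exceeds 10%, the DMC will meet every month". The only monthly rates the protocol defines are the Kaplan-Meier rates.

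A reporting minimum applies: "Rates at each monthly interval for which a minimum of 25 subjects have been implanted will be calculated". Ulcers are dated by the confirmatory endoscopy. Subjects without an ulcer who are still in the trial are censored at data cutoff.

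Routine endoscopies come at 18±4 weeks for most subjects (18-week adjustment, section 4.3.3.2.5) and at extraction after 32 weeks (4.3.3.2.6). Nothing requires the curve when the crude rate is 10% or less, and 6.1 does not say which meeting schedule then applies.

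**The concern.** A first-stage screen should not run systematically below the quantity it screens for. Here it can. A subject enters the crude denominator at 2 months but, if asymptomatic, is not routinely examined for ulcers until about 18 weeks. Until then the crude rate counts that subject as ulcer-free, while the Kaplan-Meier estimate censors the subject at the current follow-up time. Uneven follow-up of this kind is the reason to use Kaplan-Meier, and it is greatest during accrual, when a safety rule has most work to do.

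The rule can then leave its own criterion unevaluated while that criterion is met. The main consequence is that the DMC does not move to monthly meetings when the 10% limit has been crossed. The more serious but less likely consequence is a late 20% check.

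**Working it through.** **Reproducing the rule.** Coded as written, the rule returns rates for months 1, 2 and 3 in the protocol's own example (30 subjects at 3 months or more, 20 at 4 months or more), as 6.3.2 states.

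**Where the gap can arise.** At months 1 and 2 the crude rate is at least the Kaplan-Meier rate. From month 3 on it can be lower.

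**Constructed example.** Take 30 subjects at 5 months or more and 50 between 2 months and their own 18-week endoscopy. All ulcers are found at week 18, there is no other loss, and subjects with ulcers stay in the 25-subject count.
- Crude = ulcers / 80. Month-5 Kaplan-Meier = ulcers / 30, because the 50 newer subjects are censored before week 18.
- 4 ulcers: crude 4/80 = 5.0%; Kaplan-Meier 4/30 = 13.3%. The 10% limit is passed and no curve is drawn.
- 7 ulcers: crude 7/80 = 8.75%; Kaplan-Meier 7/30 = 23.3%. The 20% limit is passed and no curve is drawn.

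This example needs brisk recent accrual. Week 18 is 4.5 four-week months, so 50 subjects in the 2.5 months between the two points is 50/2.5 = 20 per 4-week month.

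**Planned pace.** The synopsis gives 30 months in total and 14 months of treatment-arm follow-up, leaving 16 months, or 16 × 52/12/4 = 17.3 four-week months. The treatment arm is 188 (section 7.2), so 188/17.3 is about 11 per 4-week month. With even accrual, at month T there are 11(T − 2) subjects in the crude denominator and 11(T − 4.5) past a week-18 endoscopy.
- Month 8: 66 in the crude denominator, 38.5 past the endoscopy, 33 at 5 months or more.
- 6 ulcers: crude 6/66 = 9.1% (no curve); Kaplan-Meier 6/38.5 = 15.6%.
- 7 ulcers: crude 7/66 = 10.6% (curve drawn); Kaplan-Meier 7/38.5 = 18.2%.

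At that point the nominal 10% meeting trigger operates at about 18%.

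**The same algebra for the 20% limit.** Crude divided by Kaplan-Meier is (T − 4.5)/(T − 2). The month-5 rate first becomes reportable at T = 5 + 25/11 = 7.3, where the ratio is 2.77/5.27 = 0.526. A crude rate of exactly 10% then corresponds to 10%/0.526 = 19.0%, and the ratio rises afterwards. So at the even planned pace, with endoscopies at week 18, ulcers found there do not pass 20% unseen.

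**Simulation.** Settings: 188 implants, about 11 per 4-week month, meetings every two months, and assumed ulcer rates written as 18 weeks/extraction.

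| Quantity | Extraction exactly week 32 | Extraction spread over weeks 30-34 |
|---|---|---|
| 10% trigger delayed, range over scenarios | 12-87% of trials | 15-63% |
| 20% check delayed, 3%/18% | 41% | 0% |
| 20% check delayed, 8%/10% | 8% | 0% |
| Suspension with → without the crude condition, 5%/5% | about 5% → 9% | no rise |

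In further runs over other accrual periods, with 20-25% of subjects having ulcers found at the 18-week endoscopy, the 20% limit was masked in 0-4% of trials at even accrual and in up to 42% when accrual accelerates.

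**The case against.** **The stronger reading.** A reader might infer that the suspension rule is often silenced. An example at month 11 of the planned pace invites this: 99 subjects at 2 months or more, 71.5 past the 18-week endoscopy and 33 extracted, with assumed rates of 3% and 18%. Events are 33 × 0.18 + 71.5 × 0.03 = 8.1, so crude is 8.1/99 = 8.2%, while the month-8 Kaplan-Meier rate is 1 − 0.97 × 0.82 = 20.5%. The documents do not support this as a general result:
- It needs every extraction at exactly week 32. Section 4.3.4 gives visits up to week 32 a ±2-week window and states no separate window for extraction. With that spread the delay is about 0%.
- In calendar months, 32 weeks is 32 × 12/52 = 7.4 months, so month 8 could not be calculated at all. The protocol does equate 32 weeks with 8 months, so the 4-week month is a fair reading.
- When extraction ulcers fall outside month 8, removing the crude condition does not recover them.
- Nothing in the documents supports 3% at 18 weeks against 18% at extraction. The excess over 20% is half a point on about 6 ulcers in 33 subjects, a standard error of √(0.18 × 0.82/33), or about 7 points.

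**Other safeguards.** The DMC sees the crude rate at each meeting and may recommend stopping (6.1). Device-related events reach the sponsor within 24 hours (6.2.4). The sponsor must suspend on suspicion of unacceptable risk (6.3.1). The stopping rule was added after FDA feedback, and a separate charter, not available here, holds further detail. These limit the harm, but none of the text available requires the curve to be calculated, and none makes the crude rate a sound screen.

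**Small-sample protection.** The crude condition does screen out some unstable early crossings. That stands, and it is a cost of removing it.

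**Conclusion.** The point holds mainly for meeting frequency. As written, the rule can leave the Kaplan-Meier rates uncalculated while they exceed 10%. At the planned pace this delays the move to monthly meetings in roughly 10-90% of simulated trials, or 15-63% when extraction is spread over weeks 30-34. The crude rate usually catches up as subjects mature, so the usual harm is delay during accrual.

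For suspension, masking is possible under the definitions but rare at even accrual. It becomes material if accrual accelerates, or if most ulcers are found at extraction and extraction falls exactly at week 32.

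Ulcer rates, their timing and the accrual pattern are assumptions, since the documents give none of them beyond the overall timetable. The simulations also take two-monthly meetings as the schedule when no curve exists, on which section 6.1 is silent. The existence of the gap rests only on the rule's own definitions; its frequency rests on these assumptions.

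**What to change.** In sections 6.1 and 6.3.2, delete the crude-rate condition and calculate the Kaplan-Meier monthly rates at every DMC meeting. The crude rate can still be reported beside them. Leave the 10% and 20% limits and the 25-subject minimum unchanged. This also settles which meeting schedule applies, because monthly rates will exist whenever the 25-subject minimum is met.

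The cost is one table per meeting from data already held, more monthly meetings, and a slightly higher chance of a suspension triggered by small numbers: 0 to about 7 percentage points in simulations, depending on accrual and extraction timing. The change does not capture ulcers found at extractions that fall outside month 8.

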### **6.4. Protocol Deviations**

All protocol deviations will be documented with the subject number and date of the protocol deviation. The following information will be documented for each protocol deviation:

- Inclusion/Exclusion exceptions or violations, including subject did not sign informed consent prior to study admission
- Follow-up visit not performed or Follow-up outside of window
- Required testing or questionnaire not performed
- Other (Describe)

## 7. STATISTICS

### 7.1. Description of Statistical Methods

#### 7.1.1. Study cohorts for analyses

The primary analysis will be based on the intent-to-treat dataset, which will include all randomized subjects according to their randomized treatment. However, any subject with an absolute contraindication to balloon implantation which was only revealed at the endoscopy procedure, and who therefore did not receive a balloon, will not be considered in analysis of efficacy.

#### 7.1.2. Primary Endpoints

The co-primary hypotheses are as follows:

1. The mean %TBL in the Spatz3 group exceeds that in the control group by 4.5%. In formal terms, this is:

$$H_0: \mu_S - \mu_C \leq 4.5\%$$

vs.

$$H_A: \mu_S - \mu_C > 4.5\%,$$

where  $\mu_S$  and  $\mu_C$  are the population mean %TBL for the Spatz3 and control groups, respectively.

2. The response rate in the Spatz3 group is superior to a performance goal of 50%, where a responder is defined as a  $\geq 5\%$  loss in total body weight at 32 weeks. In formal terms, this is:

$$H_0: \pi \leq 50\%$$

vs.

$$H_A: \pi > 50\%,$$

where  $\pi$  is the population response rate in the Spatz3 group.

All missing body weight data will first be imputed as follows. Initially, all interim missing data (missing data for which there is at least one subsequent non-missing body weight) will be linearly interpolated based on the last and subsequent non-missing body weight. If a subject in the Spatz3 group has the balloon explanted, the body weight immediately preceding the explant will be used and the subject will be treated as a dropout from that time forward, even though the subject will be followed for another 24 weeks. After the interim missing data have been interpolated, all additional missing data will be imputed using a regression method for multiple imputation. Baseline body weight, baseline BMI, subject's gender, study center, treatment group, and all non-missing body weight measurements through Week 32 will be included in the imputation model. A total of five imputed datasets will be created. The first primary endpoint, %TBL at 32 weeks, will be analyzed by an analysis of covariance that includes the effects of treatment group, study center, baseline BMI group ( $< 35 \text{ kg/m}^2$  vs.  $\geq 35 \text{ kg/m}^2$ ) and subject's gender as covariates. The parameter estimates from the five imputations

will be used to estimate a one-sided lower 97.5% confidence bound on the difference in mean %TBL (Spatz3 mean minus control mean). If this lower confidence bound exceeds the super-superiority margin of 4.5% the Spatz3 will be deemed to have super-superiority over the control group in %TBL.

The second primary endpoint will be analyzed using the same five imputed datasets created for testing the first primary endpoint, but only the data from subjects in the active treatment group. The estimated proportion of subjects with a  $\geq 5\%$  weight loss at Week 32, along with their associated variance, from each dataset will then be combined using Rubin's method to estimate the overall proportion and its variance. This proportion and its variance will then be used to estimate the one-sided lower 97.5% confidence bound on the proportion of subjects with a  $\geq 5\%$  weight loss at Week 32. If this lower confidence bound exceeds 0.50 the second primary hypothesis will be rejected, and the Spatz3 will be deemed to have met its second primary hypothesis.

As a sensitivity analysis of each co-primary endpoint, an LOCF imputation procedure will be employed in which all missing data among subjects with at least one post-randomization body weight measurement are replaced by the last non-missing value.

Secondary analyses of the primary endpoints will be per protocol and will include subjects according to the actual treatment received and will exclude subjects who did not meet the inclusion criterion of baseline BMI  $\geq 30 \text{ kg/m}^2$  and  $< 40 \text{ kg/m}^2$ .

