**Figure 1: Study Timeline**

#### 4.3.1. Screening and Eligibility Assessment

Screening will be conducted by the investigator or co-investigator and documented on the PI Intake form (*Appendix E2: CRF\_2 PI Intake*) and Screening Labs form (*Appendix E3: CRF\_3 Screening Labs*). Screening must occur no more than 30 days prior to implantation.

Screening will include the following:

1. Screening exam by investigator or co-investigator (*Appendix E2: CRF2\_PI Intake*). Includes Medical history, Current medications, Record contraceptive method for female subjects, Vital signs, Body Weight and Height, Physical exam, Evaluation of inclusion/exclusion criteria.
2. Sign Informed Consent Form (*Appendix A: Informed Consent*)
3. Dietician intake - Baseline body weight, height, ideal body weight, excess weight, BMI, (*Appendix E5: CRF5\_Dietician Intake*)
4. Laboratory tests\* plus EKG
5. Psychological evaluation (*Appendix E10: CRF10\_Consultation with Psychologist*)
6. Diabetic subject – follow up by provider or PI (*Appendix E11: CRF11\_Diabetic Patient Follow Up*)

\*Laboratory Tests (*Appendix E3: CRF3\_Screening Labs*) include:

CBC: Hgb, Hct, WBC, MCV, platelets

Chemistry panel: sodium, potassium, chloride, CO2, BUN, creatinine, glucose, SGOT/AST, SGPT/ALT, alkaline phosphatase, total bilirubin, total protein, albumin, total cholesterol, Fe/TIBC, B12, Folic Acid, 25-Hydroxy Vitamin D, TSH

Coag: Pro Time or INR, PTT

Urinalysis

HgbA1c (if diabetic)

H. Pylori Serology

Within 1 week of the screening tests, the PI will review the results and determine eligibility of the subject. The center will inform the subject of their results within 10 days of the tests. All potential subjects who pass the initial screening assessment must return for an additional visit within 7 days of the scheduled implantation procedure for the Pre-Implantation visit (*Appendix E4: CRF4\_Preimplantation Tests and Data*). This will include an assessment of the following:

- Urine pregnancy test (women of child-bearing potential)
- Medications List
- Weight (Note: This is the baseline weight that will be used for the endpoint assessments)

Subjects with a positive pregnancy test or who are taking medications listed in the exclusion criteria will be excluded from the study at this time, and will be considered to be screening failures.

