#### **4.3.3.2.6. Extraction**

The extraction procedure requires the patient to be on the following dietary restrictions:

- 72 hours prior to the procedure: Soft food only, no meat or vegetables in any form.
- 48 hours prior to the procedure: Full liquids only.
- 24 hours prior to the procedure: Clear liquids only.
- 12 hours prior to the procedure: No food or liquids by mouth.

The extraction procedure is performed under conscious sedation by the anesthetist similar to the implantation procedure. The endoscope is introduced in the usual manner. The capped valve is identified and the suture loop is grasped with a standard rat tooth grasping forceps. The scope and cap are pulled out of the mouth, wherein the cap is twisted off. A large polypectomy snare is inserted into the biopsy channel of the scope and the snare is opened and placed on the valve. Then the extension tube (provided) is connected to the valve. The scope (with snare closed on the valve) and the extension tube are lowered down the throat into the esophagus. The balloon deflation commences by utilizing the 3-way stopcock on the proximal end of the extension tube. Following completion of the deflation, the scope is pushed down to the gastro-esophageal junction to confirm complete deflation of the balloon. The snare is opened as the extension tube is pulled until the valve exits the mouth- this will bring the distal white catheter and deflated balloon edge into the open snare. The snare is closed. The scope (with snare secured around balloon/white catheter) and the stretched inflation tube are pulled out together with the balloon in tow. The scope is then reinserted to inspect for any mucosal damage.

Following the extraction procedure, all treatment subjects will be followed for an additional 24 weeks.

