#### 4.3.4. Follow-Up Schedule

Follow-up visits for treatment and control patients will occur according to the following schedule: Visits at 1 week, 2 weeks, and 4 weeks ( $\pm$  3 days), and thereafter every 4 weeks ( $\pm$  2 weeks) until primary endpoint assessment at 32 weeks. In addition, 1-2 weeks after the adjustment procedure the subject will have a follow up appointment with the PI/NP.

Each follow-up visit will include:

1. Clinical assessment by PI or nurse practitioner or physician’s assistant for both the treatment group and control group (*Appendix E6: CRF6\_Control Group PI Follow Up* or *Appendix E7: CRF7\_Treatment Group PI Follow Up*)
2. Satiety and Dietary Assessment for both the treatment group and control group - limited to 30-45 minutes per session (*Appendix E8: CRF8\_Control Group Dietician Follow Up* or *Appendix E9: CRF9\_Treatment Group Dietician Follow Up*)
3. Record adverse events, device complications, concomitant medication (*Appendix E6: CRF6\_Control Group PI Follow Up* or *Appendix E7: CRF7\_Treatment Group PI Follow Up*)
4. Weight to be done by staff (patient may not speak with weighing personnel and may not disclose if they are control or treatment arm)

Control patients will exit the study at Week 32. Treatment patients will have the device explanted and will be followed for an additional 24 weeks according to the following schedule: Visits at Week 36 ( $\pm$  3 days) and thereafter every 4 weeks ( $\pm$  2 weeks) until 56 weeks. Treatment patients who undergo balloon extraction prior to 32 weeks will be followed from the time of balloon extraction an additional 24 weeks according to the following schedule: Visits at 4 Weeks post extraction ( $\pm$  3 days) and thereafter every 4 weeks ( $\pm$  2 weeks) until 24 weeks after the extraction.

These follow-up visits for the treatment group only, will include:

1. Clinical Assessment - only at the visit 4 weeks post extraction(*Appendix E7: CRF7\_Treatment Group PI Follow Up*)
2. Satiety and Dietary Assessment (*Appendix E9: CRF9\_Treatment Group Dietician Follow Up*)

A summary of required visits and procedures for subjects who do not require an unscheduled endoscopy is shown in the following table and provided in *Appendix B: Study Visits and Master Schedule*:

Assessment / Procedure	Screening Assessments	7 Days Prior to implant	Implantation	Adjustment	Explantation	Follow-Up Assessment weeks 1-32	WEEKS 36 - 56
Informed Consent	X						
Date of birth/gender	X						

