#### **7.2. Sample size**

The true population mean %TBL in the control group is assumed to be 3.3% based on the Orbera and ReShape PMA studies. The standard deviation of %TBL is assumed to be approximately 6.6%, based on 6-month data from the Orbera PMA study. Based on these two assumptions, and a true population mean %TBL in the Spatz3 group of 10.34%, a total sample size of 240 subjects randomized 2:1 (160 in the Spatz3 group and 80 in the control group) will provide 80% power to demonstrate super-superiority of 4.5% TBL over the control at a one-sided significance of 2.5%. To account for a potential dropout rate of 15%, the final total sample size is 282 subjects randomized 2:1 (188 in the Spatz3 group and 94 in the control group).

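### The explant-weight rule is not limited to early explants, so the plan permits a weight taken after a diet and fast to serve as the Week 32 value in the Spatz3 arm only

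*Combined protocol and SAP*

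**What the plan says.** Within its missing-data rules, section 7.1.2 states: "If a subject in the Spatz3 group has the balloon explanted, the body weight immediately preceding the explant will be used". The subject then counts as a dropout from that point, despite 24 further weeks of follow-up. Gaps between observed weights are interpolated, and what remains missing is multiply imputed.

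Section 4.3.4 puts both arms on one visit schedule ending with the primary endpoint assessment at Week 32. Visits after Week 4 have a window of plus or minus two weeks. It continues: "Control patients will exit the study at Week 32. Treatment patients will have the device explanted". The visit table in that section marks body weight in an explantation column and, separately, in the column for follow-up weeks 1-32. Excess weight is also marked at explantation.

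Section 4.3.3.2.6 prescribes the preparation for extraction: soft food from 72 hours, then "48 hours prior to the procedure: Full liquids only", clear liquids from 24 hours, and finally "12 hours prior to the procedure: No food or liquids by mouth".

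Section 4.3.1 takes the baseline weight at a visit within seven days of the scheduled implantation and states no diet or fasting condition. Section 4.2 requires weighing by staff blinded to treatment group.

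**The concern.** The explant sentence has no time limit, and section 3.3 has the whole treatment group explanted at the end of the 32-week period. Read literally, it covers scheduled removals as well as early ones. The last weight before a scheduled removal can be the one recorded on the day, after the preparation.

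Reading the endpoint as the Week 32 clinic weight does not close the gap. If visit and extraction fall on the same day, the clinic weight is itself a fasted weight. If the visit falls after extraction, the explant rule substitutes the pre-explant weight. Controls face neither situation.

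The first co-primary compares the arms against a 4.5-point margin, so a shift in one arm's weights adds directly to the tested difference. The second tests the Spatz3 arm alone against a 50% goal, so there is no comparator to absorb a measurement shift. The 25% excess-weight-loss response uses the same Week 32 data.

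**Working it through.** **Inputs from the protocol.** Section 7.2: control mean 3.3, Spatz3 mean 10.34, SD 6.6, one-sided 2.5%, 160 and 80 evaluable, 15% dropout. Section 7.1.2: margin 4.5 and response goal 50%. Section 4.3.3.2.5: fill not below 300 ml nor above 1,000 ml. Section 5.1.1 gives 900 ml as the maximum; the two sections should be reconciled.

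**Assumptions, since the documents give no figure.** Preparation loss 0.5-2 kg, body weight 95 kg, fill fluid 1 kg per litre, %TBL normally distributed.

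**1. The plan's own figure.** Section 7.2 says that 240 subjects "will provide 80% power to demonstrate super-superiority of 4.5% TBL over the control". The detectable excess is 10.34 - 3.3 - 4.5 = 2.54. Controls needed: (1.960 + 0.842)² × 6.6² × (1 + 1/2) / 2.54² = 79.5, so 80, with 160 on Spatz3. SE = 6.6 × √(1/80 + 1/160) = 0.904. Power = Φ(2.54/0.904 - 1.960) = 80.2%. 240/0.85 = 282.4, against 282 stated. The design reproduces.

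**2. Net shift in Spatz3 %TBL if a prepared, pre-removal weight is used.** Shift = 100 × (preparation loss - balloon mass) / 95.

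| Preparation loss | 300 ml | 550 ml | 850 ml | 1,000 ml |
|---|---|---|---|---|
| 0.5 kg | +0.21 | -0.05 | -0.37 | -0.53 |
| 1 kg | +0.74 | +0.47 | +0.16 | 0.00 |
| 2 kg | +1.79 | +1.53 | +1.21 | +1.05 |

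The range is about -0.5 to +1.8 points. With a 900 ml maximum the lower end is 100 × (0.5 - 0.9)/95 = -0.42.

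**3. Type I error for a net shift b affecting every Spatz3 subject.**
- Co-primary 1, true difference exactly 4.5: Φ(b/0.904 - 1.960).
- Co-primary 2, true response exactly 50%: observed response π = Φ(b/6.6); error = Φ((π - 0.5)/√(π(1 - π)/160) - 1.960).

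| b (points) | Co-primary 1 | Co-primary 2 |
|---|---|---|
| -0.5 | 0.6% | 0.3% |
| 0 | 2.5% | 2.5% |
| +0.25 | 4.6% | 5.7% |
| +0.5 | 8.0% | 11.6% |
| +1.0 | 19.7% | 33.5% |
| +1.5 | 38.2% | 63.8% |

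These are rates for each endpoint singly; success needs both. If only a fraction f of subjects is affected, the mean shift is f × b. A 1-point shift in half the arm is 0.5 × 1.0 = 0.5, which gives about 8% for co-primary 1.

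**4. Explants before Week 32.** The Week 32 value is multiply imputed. The pre-explant weight enters as a predictor in the imputation model and becomes the endpoint only in the LOCF sensitivity analysis.

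**The case against.** A reader might infer that the Spatz3 endpoint weight is the fasted explant-day weight and that %TBL and response are therefore inflated. The documents do not support that.

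- The sentence is a missing-data rule. Applying it to scheduled removals would label every completing device subject a dropout, so early explant is its more natural target.
- Section 4.3.4 ties the endpoint to the Week 32 visit in both arms. No section names the explantation weight as the Week 32 value or says whether it is taken before or after removal. The weight before explant could equally be the last clinic weight. The form for baseline and follow-up weights (CRF13) might settle this, but its content is not in the text.
- Section 4.2 makes no exception to blinded weighing on procedure days. A failure of blinding there would be inference.
- The balloon opposes the preparation loss. At a 0.5 kg loss the net shift is near zero or against the device for fills of 550 ml or more.
- At the design mean of 10.34, a +1.0 shift moves expected response only from 79% to 83%, immaterial against a 50% goal. A larger recorded loss at removal would also make the 40% maintenance test harder for the device.

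All of this stands against a claim of proven inflation. It does not remove the gap: the rule has no time limit, and no section orders the weighing against the diet or sets common weighing conditions. Nor can two unmeasured device-arm effects be relied on to cancel.

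**Conclusion.** The concern holds as an open definition of a co-primary measurement, with possible bias in the device arm only. It is not an established bias in the device's favor. The net shift of about -0.5 to +1.8 %TBL points rests on the assumed preparation loss, body weight and fluid density. Error rates of about 8% and 20% for co-primary 1 apply only at net shifts of +0.5 and +1.0 in every Spatz3 subject; at -0.5 the test is conservative, at 0.6%. For subjects explanted before Week 32, the effect is confined to the imputation model and the LOCF analysis. Because plausible positive shifts could multiply the nominal 2.5% several times, the endpoint weight should be fixed before outcome data are examined.

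**What to change.** 1. In 7.1.2, limit the explant rule to explants that occur before the Week 32 visit.
2. In 7.1.2 and 4.3.4, define the endpoint weight in both arms as the blinded clinic weight at the Week 32 visit, taken for Spatz3 subjects before the pre-extraction diet starts. For early explants, use the last scheduled-visit weight before the preparation as the final observed value.
3. Keep procedure-day weights out of the endpoints and the imputation model.
4. Add a sensitivity analysis that subtracts the recorded balloon fill mass from on-balloon weights. The clinic weight still includes the balloon, so steps 1-3 do not deal with it.

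The cost is a few sentences. The Week 32 weight is already scheduled, the sample size stays at 240 evaluable and 282 randomized, and the extraction procedure is unchanged. Some subjects would attend the visit and the extraction on different days, and the estimated device effect may become slightly less favorable.
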